6.4. Other Efficacy Endpoints Analysis

The exploratory endpoints for the double-blind period are as follows:

- proportion of patients reaching at least 75% reduction in the monthly average number of migraine days during the 12-week period after the 1st dose of study drug
- proportion of patients reaching total (100%) response (no headache) during the 12-week period after the 1st dose of study drug
- proportion of patients reaching total (100%) response (no headache) for at least one month during the 12-week period after the 1st dose of study drug
- mean change from baseline (28-day run-in period) in the monthly average number of headache hours of at least moderate severity during the 12-week period after the 1st dose of the study drug
- proportion of patients reaching at least 50% reduction in the number of migraine days during the 4-week period after the 1st dose of study drug for whom this level of effect is sustained throughout the 12-week period after the 1st dose of study drug
- proportion of patients reaching at least 75% reduction in the number of migraine days during the 4-week period after the 1st dose of study drug for whom this level of effect is sustained throughout the 12-week period after the 1st dose of study drug
- mean change from baseline (28-day run-in period) in the monthly average number of days with nausea or vomiting during the 12-week period after the 1st dose of study drug

Statistical Analysis Plan

- mean change from baseline (28-day run-in period) in the monthly average number of days with photophobia and phonophobia during the 12-week period after the 1st dose of study drug
- mean change from baseline (28-day run-in period) in the monthly average number of days of use of migraine-specific acute headache medications (triptans and ergot compounds) during the 12-week period after the 1st dose of study drug
- mean change from baseline (28-day run-in period) in the number of migraine days during the 12-week period after the 1st dose of study drug for patients who failed topiramate for migraine in the past
- mean change from baseline (28-day run-in period) in the number of migraine days during the 12-week period after the 1st dose of study drug for patients who failed onabotulinumtoxinA for migraine in the past
- mean change from baseline (28-day run-in period) in the number of migraine days during the 12-week period after the 1st dose of study drug for patients who failed valproic acid for migraine in the past
- mean change from baseline (28-day run-in period) in the number of migraine days during the 12-week period after the 1st dose of study drug for the subset of patients who failed 2 to 3 classes of preventive medications and valproic acid for migraine in the past
- proportion of patients reaching at least 50% reduction in the monthly average number of migraine days during the 12-week period after the 1st dose of fremanezumab for the subset of patients who failed 2 to 3 classes of preventive medications and valproic acid for migraine in the past
- mean change from baseline (day 0) in disability score, as measured by the HIT-6, at 4 weeks after administration of the 3rd dose of study drug
- mean change from baseline (day 0) in disability score, as measured by the MIDAS questionnaire, at 4 weeks after the administration of the 3rd dose of study drug
- mean change from baseline (day 0) in quality of life, as measured by the MSQOL questionnaire, at 4 weeks after administration of the 3rd dose of study drug
- mean change from baseline (day 0) in the health status, as measured by the EQ-5D-5L questionnaire at 4 weeks after administration of the 3rd dose of study drug
- mean change from baseline (day 0) in patient depression status, as measured by the PHQ-2 and PHQ-9, at 4 weeks after administration of the 3rd dose of study drug
- mean change from baseline (day 0) in patient work productivity and activity impairment, as measured by the WPAI questionnaire, at 4 weeks after administration of the 3rd dose of study drug
- mean change from baseline (day 0) of patient satisfaction, as measured by the PGIC scale, at 4 weeks after the 3rd dose of study drug

The exploratory endpoints for the open-label period are as follows:

- mean change from baseline (28-day run-in period) in the monthly average number of migraine days during the 12-week period after the 4th dose of fremanezumab
- proportion of patients reaching at least 50% reduction from baseline (28-day run-in period) in the monthly average number of migraine days during the 12-week period after the 4th dose of fremanezumab
- mean change from baseline (28-day run-in period) in the monthly average number of headache days of at least moderate severity during the 12-week period after the 4th dose of fremanezumab
- mean change from baseline (28-day run-in period) in the monthly average number of days of use of any acute headache medications during the 12-week period after the 4th dose of fremanezumab
- proportion of patients reaching at least 75% reduction from baseline (28-day run-in period) in the monthly average number of migraine days during the 12-week period after the 4th dose of study drug
- proportion of patients reaching total (100%) response (no headache) during the 12-week period after the 4th dose of study drug
- proportion of patients reaching total (100%) response (no headache) for at least one month during the 12-week period after the 4th dose of study drug
- mean change from baseline (28-day run-in period) in the monthly average number of headache hours of at least moderate severity during the 12-week period after the 4th dose of the study drug
- proportion of patients reaching at least 50% reduction from baseline (28-day run-in period) in the number of migraine days during the 4-week period after the 4th dose of study drug for whom this level of effect is sustained throughout the 12-week period after the 4th dose of study drug
- proportion of patients reaching at least 75% reduction from baseline (28-day run-in period) in the number of migraine days during the 4-week period after the 4th dose of study drug for whom this level of effect is sustained throughout the 12-week period after the 4th dose of study drug
- mean change from baseline (28-day run-in period) in the monthly average number of days with nausea or vomiting during the 12-week period after the 4th dose of study drug
- mean change from baseline (28-day run-in period) in the monthly average number of days with photophobia and phonophobia during the 12-week period after the 4th dose of study drug
- mean change from baseline (28-day run-in period) in the monthly average number of days of use of migraine-specific acute headache medications (triptans and ergot compounds) during the 12-week period after the 4th dose of study drug

Statistical Analysis Plan

- mean change from baseline (28-day run-in period) in the number of migraine days during the 12-week period after the 4th dose of study drug for patients who failed topiramate for migraine in the past
- mean change from baseline (28-day run-in period) in the number of migraine days during the 12-week period after the 4th dose of study drug for patients who failed onabotulinumtoxinA for migraine in the past
- mean change from baseline (28-day run-in period) in the number of migraine days during the 12-week period after the 4th dose of study drug for patients who failed valproic acid for migraine in the past
- mean change from baseline (28-day run-in period) in the number of migraine days during the 12-week period after the 4th dose of study drug for patients who failed 2 to 3 classes of preventive medications in addition to valproic acid for migraine in the past
- proportion of patients reaching at least 50% reduction from baseline (28-day run-in period) in the monthly average number of migraine days during the 12-week period after the 4th dose of fremanezumab for patients who failed 2 to 3 classes of preventive medications in addition to valproic acid for migraine in the past
- mean change from baseline (day 0) in disability score, as measured by the HIT-6, at 4 weeks after administration of the 6th dose of study drug
- mean change from baseline (day 0) in disability score, as measured by the MIDAS questionnaire, at 4 weeks after the administration of the 6th dose of study drug
- mean change from baseline (day 0) in quality of life, as measured by the MSQOL questionnaire, at 4 weeks after administration of the 6th dose of study drug
- mean change from baseline (day 0) in the health status, as measured by the EQ-5D-5L questionnaire at 4 weeks after administration of the 6th dose of study drug
- mean change from baseline (day 0) in patient depression status, as measured by the PHQ-2 and PHQ-9, at 4 weeks after administration of the 6th dose of study drug
- mean change from baseline (day 0) in patient work productivity and activity impairment, as measured by the WPAI questionnaire, at 4 weeks after administration of the 6th dose of study drug
- mean change from baseline (day 0) of patient satisfaction, as measured by the PGIC scale, at 4 weeks after the last 6th dose of study drug

The exploratory endpoints for both the double-blind and open-label periods are as follows:

- to evaluate the immunogenicity response of fremanezumab and the impact of ADAs on clinical outcomes in patients exposed to sc fremanezumab.
- to explore the relationship between genetic polymorphisms (including those within the CGRP receptor-ligand complex, in migraine-associated susceptibility genes, and in as-yet undiscovered loci) versus migraine onset/severity, adverse events to medication and fremanezumab efficacy

- to explore the relationship between exploratory biofluid biomarkers versus fremanezumab concentrations, adverse events and fremanezumab efficacy

6.4.1. Electronic Headache Diary Data

6.4.1.1. Definition

The percent reduction in the monthly average number of migraine days during the 12-week period after the 1st dose of fremanezumab will be calculated by formula (4) in Section 6.1. The patient is considered as a responder reaching 50%, 75% or 100% reduction if his/her percent reduction is 50% or more, 75% or more, or 100% respectively. If a patient is early discontinued from the study, he/she will be counted as a non-responder. Similar definition will be applied to calculate the proportion of patients reaching at least 50%, 75% or 100% reduction in the monthly average number of migraine days during the 12-week period after the 4th dose of fremanezumab. Similar definition will be applied to calculate the proportion of patients reaching at least 50% reduction in the monthly average number of migraine days during the 12-week period after the 1st dose of fremanezumab for the subset of patients who failed 2 to 3 classes of preventive medications and valproic acid for migraine in the past and to calculate the proportion of patients reaching at least 50% in the monthly average number of migraine days during the 12-week period after the 4th dose of fremanezumab for the subset of patients who failed 2 to 3 classes of preventive medications in addition to valproic acid for migraine in the past.

The percent reduction in the monthly average number of migraine days for at least 1 month during the 12-week period after the 1st dose of fremanezumab will be calculated by formula (4) where the postbaseline value will be the number of migraine days prorated to 28 days for months 1, 2, and 3. If the patient has 100% reduction or more for at least 1 month, he/she will be considered a responder for that month during the 12-week period after the 1st dose of fremanezumab. Similar definition will be applied to calculate the percent reduction in the monthly average number of migraine days for at least 1 month during the 12-week period after the 4th dose of fremanezumab.

The percent reduction on the monthly average number of migraine days during the 4-week period after each dose for months 1, 2, and 3 will be calculated by formula (4) in Section 6.1 where the postbaseline value will be the number of migraine days prorated to 28 days for month 1, month 2, and month 3, respectively. If the patient has 50% reduction or more in month 1, he/she will be considered a responder during the 4-week period after the 1st dose of study drug. In addition, if the patient also has 50% reduction or more in month 2 and month 3, he/she is a responder for months 2 and 3, and the level of effect is sustained throughout the 12-week period after the 1st dose of study drug for this patient. Similar definition will be applied to calculate the proportion of patients reaching at least 75% reduction in the number of migraine days during the 4-week period after the 1st dose of study drug for whom this level of effect is sustained throughout the 12-week period after the 1st dose of study drug. Similar definition will be applied to calculate the proportion of patients reaching 50% and 75% reduction in the number of migraine days during the 4-week period after the 4th dose of fremanezumab.

The change from baseline in the monthly average number of days or hours of exploratory efficacy variables for the double-blind period (e.g., headache hours of at least moderate severity, days with nausea or vomiting, days with photophobia and phonophobia, days of use of migraine-

specific acute headache medications [triptans and ergot compounds], migraine days for patients who failed topiramate for migraine in the past, migraine days for patients who failed onabotulinumtoxinA for migraine in the past, migraine days for patients who failed valproic acid for migraine in the past, and migraine days for the subset of patients who failed 2 to 3 classes of preventive medications and valproic acid for migraine in the past) during the 12-week period after the 1st dose of fremanezumab and the change from baseline in the monthly average number of days or hours of exploratory efficacy variables for the open-label period (e.g., headache days of at least moderate severity, days of use of any acute headache medications, headache hours of at least moderate severity, days with nausea or vomiting, days with photophobia and phonophobia, days of use of migraine-specific acute headache medications [triptans and ergot compounds], migraine days for patients who failed topiramate for migraine in the past, migraine days for patients who failed onabotulinumtoxinA for migraine in the past, migraine days for patients who failed valproic acid for migraine in the past, and migraine days for patients who failed 2 to 3 classes of preventive medications in addition to valproic acid for migraine in the past) during the 12-week period after the 4th dose of fremanezumab will be derived similar to the primary efficacy variable using the electronic diary data collected through the corresponding headache diary questions ([Appendix A](#)). The baseline values and the postbaseline values will be derived using formula (3) and (1) in Section 6.2.1, and the change is calculated as *postbaseline value – baseline value*. Similar definition will be applied for the change from baseline in the monthly average number of migraine days during the 12-week period after the 4th dose of fremanezumab.

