The **monthly average number of days or hours** of efficacy variables (e.g., days of headache with at least moderate severity, migraine days, days of headache with any severity, total hours of headache with any severity, total hours of headache with at least moderate severity, days of use of any acute headache medications, days with nausea or vomiting, days with photophobia and phonophobia etc.) **during the 12-week period** after the 1st dose of study drug will be derived and normalized to **28** days equivalent using the following formula.

$$\frac{\sum \text{Days or hours of efficacy variable over the 12 week period}}{\sum \text{Days with assessments recorded in the eDiary for the 12 week period}} \times 28 \quad (1)$$

The **monthly number of days or hours** of efficacy variables **during a 4-week period** after each dose will be derived and normalized to **28** days equivalent using the following formula, where monthly data separated by each visit of study drug dosing will be used.

$$\frac{\sum \text{Days or hours of efficacy variable during the 4 week period}}{\sum \text{Days with assessments recorded in the eDiary for the 4 week period}} \times 28 \quad (2)$$

The **baseline values** will be calculated using all data collected in the run-in period.

$$\frac{\sum \text{Days or hours of efficacy variable during the run – in period}}{\sum \text{Days with assessments recorded in the eDiary for the run – in period}} \times 28 \quad (3)$$

The **percentage of reduction** in the monthly average number of an efficacy variable will be calculated as

$$\frac{\text{baseline value} - \text{postbaseline value}}{\text{baseline value}} \times 100\% \quad (4)$$

where the baseline value is calculated by formula (3) and the postbaseline value in the equation is calculated by formula (1) for the variables **during the 12-week period** or by formula (2) for the variables **during the 4-week period** after each dose for months 1, 2 and 3.

The **baseline values** for calculating the change from baseline of the weekly number of days of the efficacy variables will use all data collected in the run-in period and be calculated as

$$\frac{\sum \text{Days of efficacy variable during the run – in period}}{\sum \text{Days with assessments recorded in the eDiary for the run – in period}} \times 7 \quad (5)$$

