17. CHANGES TO ANALYSES SPECIFIED IN THE STUDY PROTOCOL

The planned interim analyses (see Section 2.5.1) have been updated to indicate that there will be 2 interim database locks and a final database lock. This was updated as clarification.

The PP analysis set definition (see Section 3.4) has been modified to update “completing the study” to “completing the double-blind treatment period”. This change has been made as this analysis set is only used for the primary and secondary efficacy endpoints which are for the double-blind treatment period only. Additional details have also been added regarding compliance and incorrect study drug administered. A statement has also been added to clarify that a blinded data review meeting will be conducted prior to the interim database lock to determine the exclusion of the patients.

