APPENDIX A. E-DIARY QUESTIONNAIRE

The following questions are referring to yesterday (00:00 - 23:59)	
A1	Did you experience a headache of any severity yesterday?
A2	Did you have at least four (4) consecutive hours of headache yesterday?
A3	Did you have at least two (2) consecutive hours of headache yesterday?
A4	What was the greatest severity that your headache reached yesterday at any time?
A5	How many total hours did you have a headache(s) of any severity yesterday?
A6	How many total hours did you have a headache(s) of moderate or severe intensity yesterday?

The following questions are referring to yesterday (00:00 - 23:59) AT THE TIME WHEN YOUR HEADCAHE REACHED THE WORST SEVERITY	
B1	Was it worse on one side of the head than on the other, and/or limited to one side of the head?
B2	Was it pounding, pulsating, or throbbing?
B3	Was it made worse by routine activities such as walking or climbing stairs?
B4	Did you have nausea, or get sick to your stomach?
B5	Did light bother you more than when you didn't have a headache (did you experience photophobia)?
B6	Did sounds bother you more than when you didn't have a headache (did you experience phonophobia)?
The following questions are referring to yesterday (00:00 - 23:59)	
B7	Did you experience something like seeing spots, stars, lines, flashing lights, zigzag lines, or "heat waves" around the time of your headache? (This is different from "light bothers you")
B8	Did you have feelings such as numbness or tingling in any part of your body or face around the time of your headache?
B9	Did you experience something like seeing spots, stars, lines, flashing lights, zigzag lines, or "heat waves" similar to those you may have seen when you have a headache? (This is different from "light bothers you")
B10	Did you have feelings such as numbness or tingling in any part of your body or face, similar to what you may have felt when you have a headache?
C0	Did you take any medications yesterday for your headache/migraine?
C1	Were any of the following Medications taken yesterday?
	Local list of Triptans, Ergots and Opioid combinations, Presented in groups of 5 per screen, with Yes / No option to answer.

For the following questions please do not consider any medications you listed in the above questions.	
D1	Did you use any other prescription medications (i.e., opioids) in an effort to get relief from your headache/migraine?

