APPENDIX B. LOGICS FOR ENDPOINTS DERIVATION

Migraine day: 1 of the following 5 options Primary endpoint			
OPTION 1			
Part 1	1	A1	YES
	2	A2	YES
		AND	
		TWO OF THE FOLLOWING	
Part 2	1	A4	Mod-S
	2	B1	YES
	3	B2	YES
	4	B3	YES
		AND	
		ONE OF THE FOLLOWING	
Part 3	1	B4	YES
	2	B5	YES
		AND	
	B6	YES	
OPTION 2			
1	A1	YES	
2	C0	YES	
3	C1	YES	
4	C1	ERGOT OR TRIPTAN	
OPTION 3			
1	A1	YES	
2	C0	YES	
3	D1	YES	
4	D1	ERGOT OR TRIPTAN	
OPTION 4			
1	A1	YES	
		AND	
		ONE OF THE FOLLOWING	
1	B7	YES	
		OR	
2	B8	YES	
OPTION 5: PROBABLE MIGRAINE			

If **Part 1** and **Part 2** met from option 1, **Part 3** needs ONLY one of the following:

Part 3		B5	YES
		B6	YES

If **Part 1** and **Part 3** met from option 1, **Part 2** needs ONLY one of the following:

[figure not shown]
Part 2	1	A4	Mod-S
	2	B1	YES
	3	B2	YES
	4	B3	YES

If **Part 2** and **Part 3** met from option 1, **Part 1** needs ONLY the following:

[figure not shown]
Part 1	1	A1	YES
---------------	---	----	-----

Headache day of at least moderate severity: 1 of the following 3 options		
OPTION 1		
1	A1	YES
2	A2	YES
3	A4	Moderate or Severe
OPTION 2		
1	A1	YES
2	C0	YES
3	C1	YES
4	C1	ERGOT OR TRIPTAN
OPTION 3		
1	A1	YES
2	C0	YES
3	D1	YES
4	D1	ERGOT OR TRIPTAN

[figure not shown]

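### The four 'no headache' total-response endpoints are derived from migraine days, so patients with headaches can be counted as headache-free; SAP 6.3.1.1 also cites a wrong formula for two month-1 endpoints

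*SAP*

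**What the plan says.** **Labels.** SAP 6.4 lists, for the double-blind period, the "proportion of patients reaching total (100%) response (no headache) during the 12-week period after the 1st dose of study drug" and, for the open-label period, the "proportion of patients reaching total (100%) response (no headache) during the 12-week period after the 4th dose of study drug". Each has a companion endpoint for at least one month within the same 12 weeks. Protocol 9.5.3 uses the same labels.

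**Derivation.** SAP 6.4.1.1 is the only place that defines a 100% response. It applies formula (4), the percentage reduction from baseline, to migraine days after the first dose. It then extends the rule to the period after the fourth dose, as the proportion of patients "reaching at least 50%, 75% or 100% reduction in the monthly average number of migraine days". The one-month versions take migraine days prorated to 28 days, month by month: "If the patient has 100% reduction or more for at least 1 month, he/she will be considered a responder for that month".

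**Other variables in the SAP.** Appendix A asks every day: "Did you experience a headache of any severity yesterday" (item A1). SAP 4.2 lists headache days of any severity at baseline, separately from migraine days. SAP 6.1 lists "days of headache with any severity, total hours of headache with any severity" among the 12-week variables. Appendix B gives moderate-or-worse headache days their own logic, separate from the migraine-day logic: "Headache day of at least moderate severity: 1 of the following 3 options".

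**Declared changes.** Section 17 begins "The planned interim analyses (see Section 2.5.1) have been updated" and then covers the per-protocol set. It says nothing about total response.

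**Formula citation.** For the month-1 changes in migraine days and in moderate-or-worse headache days, SAP 6.3.1.1 cites formulas (2) and (1), placed in Section 6.2.1. The formulas are in fact in Section 6.1, where (1) is the 12-week post-baseline value, (2) the 4-week post-baseline value and (3) the run-in baseline.

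**The concern.** A label that promises no headache has been attached to a rule that checks only for no migraine day. Migraine days are a narrower set than headache days, so a patient with recorded headaches, including ones the SAP itself classes as moderate or severe, can enter the table as having none. Complete headache freedom is an easily quoted result, and its rate would be overstated in whichever arm such patients fall.

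The citation slip is smaller in substance, but it sits on endpoints that are tested. The two month-1 changes are third and sixth in the SAP 6.3 order that Section 7 uses for hierarchical testing. Read literally, their derivation contains no baseline.

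**Working it through.** **1. Is every migraine day a headache day?** Yes. All five migraine-day options in Appendix B require A1 = YES plus something more. Replacing migraine days by A1 days can therefore only remove total responders, never add them.

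**2. Can a headache day fail to be a migraine day?** Take A1 = YES, no triptan or ergot, and B7 = B8 = NO, so that only options 1 and 5 can apply. The remaining items are A2 (4 consecutive hours), A4 (mild, or moderate/severe) and B1 to B6, giving 2^8 = 256 patterns. Each combination of A2 and A4 has 8 settings of B1–B3 times 8 settings of B4–B6, which is 64. Part 3 of option 1 (B4, or B5 with B6) holds in 5 of the 8 settings of B4–B6. At least one of B4–B6 is YES in 7 of 8.

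| A2 | A4 | Migraine-day patterns | Not migraine days |
|---|---|---|---|
| NO | mild | two or more of B1–B3 (4) × 5 = 20 | 64 − 20 = 44 |
| NO | moderate/severe | one or more of B1–B3 (7) × 5 = 35 | 64 − 35 = 29 |
| YES | mild | 4 × 7 + 3 × 5 = 43 | 64 − 43 = 21 |
| YES | moderate/severe | 7 × 7 + 1 × 5 = 54 | 64 − 54 = 10 |

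Total: 152 migraine-day patterns and 44 + 29 + 21 + 10 = 104 that are not. Of the 104, 65 are mild (of 128) and 39 moderate or severe (of 128). The last row is exactly the set that meets option 1 of the SAP's moderate-or-worse headache day. One member: A1, A2 and B1–B3 YES, A4 severe, B4–B6 NO.

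**3. What happens to one patient?** Assume 14 migraine days per 28 at baseline, then 84 recorded diary days with 0 migraine days and 6 non-migraine headache days. Formula (4) gives (14 − 0)/14 = 100%, so the patient is a total responder. The same patient's headache-day value by formula (1) is 6/84 × 28 = 2.0 per 28 days. With 1 or 24 such days it would be 0.33 or 8.0, and the classification would be unchanged.

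**4. How large could the overstatement be?** If a share x of counted total responders has at least one such headache day, the reported rate is 1/(1 − x) times the headache-free rate: 1/0.90 = 1.11, 1/0.75 = 1.33 and 1/0.50 = 2.00 for x = 10%, 25% and 50%. These values of x are assumptions; the documents support none of them.

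**5. The month-1 citation.** Assume a baseline of 14 and fully recorded months of 10, 9 and 8, so formula (1) gives (10 + 9 + 8)/3 = 9.

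- Intended, (2) − (3): 10 − 14 = −4.
- As cited, (2) − (1): 10 − 9 = +1, or −1 with the order reversed.

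For the treatment contrast in migraine days, assume the SAP 2.4 planning effect of 1.8 days holds in each of months 1 to 3. The intended derivation estimates 1.8. The literal one estimates 1.8 − (1.8 + 1.8 + 1.8)/3 = 0.

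**The case against.** The best counter-argument is that total response is simply the top step of the responder scale. The protocol defines responders through migraine days and carries that method over to the exploratory proportions. The endpoint follows directly after the 75% migraine-day responder, and the words about headache may be a loose gloss. The SAP rule is explicit and reproducible, the SAP Introduction says the SAP prevails over the protocol, the same rule applies in every arm, and no alpha is spent.

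Most of this bears on importance. The shorthand reading is weak because SAP 4.2 and 6.1 keep headache days of any severity apart from migraine days, and neighbouring endpoints say migraine days when they mean them. Precedence settles which rule is run but does not make the label true, and the mismatch also lies within the SAP, between 6.4 and 6.4.1.1. The exploratory status stands. So does the point that pattern counts and assumed values of x show possibility and direction, not size.

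On the citation, the objection that this is clerical is right. The same sentence defines change as post-baseline minus baseline, formula (2) is correctly cited, and SAP 4.2, 6.1 and 6.3 all fix the run-in as baseline. The by-month outputs in SAP 6.2.3.1 and 6.4.1.2 would probably expose a literal misreading. The 1.8-day planning value covers migraine days only, so the 0-versus-1.8 comparison should not be carried over to moderate-or-worse headache days.

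One further point stands: with the 10-day diary minimum, a month with 10 recorded headache-free days still counts, with 18 days unknown, even after rederivation.

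**Conclusion.** The concern holds. As written, SAP 6.4.1.1 can count patients with recorded headaches as having none, for all four total-response endpoints. The direction is certain, because every migraine day requires A1 = YES: the reported rate equals or exceeds the headache-free rate. The size is unknown, since it depends on how many patients without migraine days still record other headaches, and the documents do not say. No direction of bias in the comparison between arms is claimed. Because these endpoints are exploratory, this is something to correct before analysis and not a threat to the trial's conclusions.

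The formula citation in SAP 6.3.1.1 is also wrong, but its intended reading is clear. The primary endpoint, the 12-week secondary endpoints and the month-1 responder endpoint are unaffected.

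**What to change.** Before the first interim lock, by which SAP 2.5.2 requires amendments to be approved:

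1. In SAP 6.4.1.1, define total response as A1 = NO on every recorded day, over the 12 weeks or within a month, keeping the existing minimum-diary and early-discontinuation rules. Alternatively, rename the four endpoints as a 100% reduction in migraine days and list that in Section 17.
2. In SAP 6.3.1.1, cite formula (2) for the month-1 value and formula (3) for baseline. Correct the three formula pointers from Section 6.2.1 to Section 6.1: two in 6.3.1.1 and one in 6.4.1.1.

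The cost is SAP wording and minor programming. A1 is already collected daily and any-severity headache days are already derived. Sample size, alpha and test order do not change.
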